#### 10.3.4 **Genetic Analyses**

This study also seeks to obtain blood samples at baseline and 6 months to evaluate associations between genes, demographic and clinical characteristics and patient outcomes (e.g., HRQoL response/non-response, symptoms). While it is becoming increasingly clear that genetic variation plays a role in HRQoL and symptom experience, the current evidence is limited so investigators have called for the incorporation of biological data in new symptom science research [33]. By collecting and storing samples from PROMISE participants we will generate a valuable resource to answer questions about the association between genotype, gene expression and DNA methylation and HRQoL and symptom experience. These analyses (to be funded separately) will use the most up-to-date methods. They will help us to interpret the magnitude of the intervention effect and to identify possible reasons for heterogeneity in the outcomes of participants. We also hope the results will inform future development of personalised supportive care interventions that meet the varied individual needs of people with cancer. For example, the results may lead to the development of a prognostic test for whether an individual is likely to experience debilitating side effects from treatment. This information can then be used in treatment decision making as well as identifying those who may need greater supportive care or vigilance in disease monitoring.

#### 10.3.5 **Implementation Outcomes:**

These analyses will be largely descriptive combining usage statistics and the results from the qualitative stakeholder interviews. The goal is not to prove superiority but to show that it is feasible for sites to implement the tools and to identify barriers and enablers to this. Interview transcripts will be analysed inductively and deductively through content analysis and using the Consolidated Framework for Implementation Research (CFIR) {Ref}, thereby enhancing our ability to explore reasons for successes and challenges to effective implementation. Coding will be performed with the assistance of the NVivo12 software program. To ensure rigour and agreement in the data, two researchers will code the transcripts independently and discuss any discrepancies. After all interviews have been coded, the analysis will be reviewed by a third researcher. Final results will be discussed between the three researchers involved in the analysis to reach consensus on data interpretation and major themes.

**REACH & Representativeness:** We will describe participation rates, compare the characteristics of the study population to state-wide statistics and describe factors associated with non-participation.

**ADOPTION:** We will describe patient, partner/carer and healthcare provider perspectives on the e-PROM tools and will assess their ease of use using the System Usability Scale.

**IMPLEMENTATION:** CFIR will allow a detailed exploration of the following implementation domains: Intervention Characteristics, Outer Setting, Inner Setting, Characteristics of Individuals, and the Process of Implementation. Within the intervention group, we will also calculate the total numbers and proportions of eligible e-PROMs completed prior to each medical appointment (N, %), the proportion of e-PROM items completed (%), the frequency of clinician access to e-PROM data (N, %), overall and by subgroups defined as above. We will also calculate the average length of medical appointments at the cancer centre and the rate (per patient-year) of GP and specialist visits made by participants and compare these across the intervention and control groups.

**MAINTENANCE (Sustainability):** We will calculate the proportion of the clinics, intervention participants, and clinicians using the e-PROMs at the end of the study, 6 months and 12 months after study completion. We will also assess whether the implementation of the e-PROM tools was cost-effective as this will be key for sustainability (See 10.3.6).

#### 10.3.6 *Economic Outcomes:*

We will compare the costs and health benefits associated with the e-PROM intervention from the health system perspective. The health benefits will be: (1) quality-adjusted life years quantified using the EQ-5D (QALYs); and (2) hospitalisations avoided. Incremental cost-per-effect ratios will be generated which represent the additional cost and health benefits (QALYs, hospitalisations avoided) for the intervention, compared with usual care.

Generalised estimating equations will assess both time and treatment effects and allow for non-parametric and missing data. Using the area-under-the-curve method and health utility scores at each time point, a single QALY for each person will be calculated at the last time point[34]. One-way and probabilistic sensitivity analyses to address data uncertainty will be performed using TreeAge Pro for Healthcare (TreeAge Software Inc). We will consider a Markov microsimulation model informed by our clinical data.

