#### **3.4 Expected Duration of Study**

The active component of the study is expected to run for up to 3 years. It is anticipated that it will take 12 months to recruit participants and that the intervention and active follow-up will continue for up to 2 years. [Funding is currently available for 1.5 years follow-up but, if additional funding can be secured, we will continue active follow-up for an additional 6 months for a total of 2 years.]

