### 10.2 **Sample Size Considerations**

Our sample-size has been calculated to achieve a minimum 80% power ( $\alpha=0.05$ ) for our primary outcomes.

- Emergency presentations (measured from linked data that will be close to complete): Previous studies have reported reductions of 17-30% ([9] and personal communication). Assuming a similar baseline rate (1.09/person-year), we require 242 participants per group to detect a 20% reduction with 18 months follow-up.

- HR-QOL: To detect minimally-important differences (where there is no defined minimally-important difference we have used 0.5 standard deviations as recommended [32] we require 70-150 patients per group depending on the outcome. A sample of 200 per group will give >90% power for the primary outcomes in the full population and ~80% power for analyses stratified by e-PROM tool.

Allowing for up to 30% drop-outs (death or withdrawal), we will recruit a minimum of 572 participants (286 per group). We estimate that more than 2000 eligible patients will attend the study hospitals during a 12-month period (data from the Queensland Oncology Analysis System) thus this target is feasible.

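### Section 10.3.6 credits GEE with handling missing data, but unweighted GEE does so only under restrictive conditions and cannot complete a per-person QALY when EQ-5D is missing

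*Protocol*

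**What the plan says.** Protocol section 10.3.6 names one method for incomplete economic data: "Generalised estimating equations will assess both time and treatment effects and allow for non-parametric and missing data". It gives no weighting, imputation, missingness assumption or working correlation. It then says that, from utilities at each visit and by area under the curve, "a single QALY for each person will be calculated at the last time point". The sensitivity analyses named are of another kind: "One-way and probabilistic sensitivity analyses to address data uncertainty will be performed using TreeAge Pro for Healthcare".

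Related statements elsewhere in the protocol:

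- Appendix A schedules EQ-5D at months 0, 3, 6, 12, 18 and 24. Section 3.4 says "Funding is currently available for 1.5 years follow-up"; month 24 depends on further funding.
- Section 2.3.5 takes costs from linked administrative collections. Section 4.4.2 continues passive follow-up after partial withdrawal.
- Sections 2.3.3 and 7.1.3 collect the date of death.
- Section 10.3.2 adjusts the FACT-G, HADS and MSAS models for baseline score and stratification factors. Section 10.3.6 does not mention adjustment.
- Section 10.2 sizes the trial "Allowing for up to 30% drop-outs (death or withdrawal").

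**The concern.** The sentence on GEE is a positive statement about a method, so it is more than a detail awaiting the SAP. An analysis plan that follows it would treat missing EQ-5D as already dealt with.

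Two things are wrong with it. First, the property claimed does not hold in general. Unweighted GEE needs data missing completely at random, or missingness that depends only on covariates in the model. Here some patients have palliative treatment intent, only those with a life expectancy under 3 months are excluded, and follow-up lasts at least 18 months. Worsening health is therefore a plausible reason for not returning a questionnaire. Second, GEE on repeated utilities does not repair the quantity that the section goes on to define, which is a single QALY for each person.

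Cost-effectiveness is a secondary outcome in the Protocol Summary, and section 10.3.5 calls it key for sustainability. A cost-per-QALY ratio is sensitive to small changes in its denominator.

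**Working it through.** **1. The plan's own figure.** Section 10.2 says that "A sample of 200 per group will give >90% power for the primary outcomes in the full population". Inflating 200 for 30% loss gives 200 / (1 − 0.30) = 285.7, rounded up to 286 per group and 572 in total, as stated. The 30% is therefore a planning ceiling for death and withdrawal combined. Section 10.2 gives no sample size, effect or standard deviation for the economic outcome.

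**2. What the per-person QALY needs.** With visits at 0, 3, 6, 12 and 18 months, the trapezoid weights in years are 0.125, 0.25, 0.375, 0.5 and 0.25, which sum to 1.5. For a living person without month 18, the area from month 12 to 18 is undetermined: 0.5 of 1.5 years, a third of the horizon. An interior gap can be bridged by a straight line, but that is itself an unstated imputation. GEE fitted to the repeated utilities estimates mean profiles by arm and leaves the individual's area incomplete. GEE fitted to the QALY itself has one record per person, so a missing QALY simply drops out.

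**3. Does the missingness mechanism matter?** This was checked by simulation. Every input except the group size and visit times is an assumption, because the documents give no utility data.

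- Inputs: 286 per group; mean utility 0.72; between-person SD 0.15; within-person SD 0.10; utility gain 0.03 from month 3; about 30–33% lost by month 18 (none in the first row of the table).
- True QALY gain: 0.03 × (0.25 + 0.375 + 0.5 + 0.25) = 0.03 × 1.375 = 0.041.

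Bias of the complete-case area-under-the-curve difference (1,500 replicates):

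| Loss | Unadjusted | Adjusted for baseline utility |
|---|---|---|
| None | 0.000 | 0.000 |
| Completely at random | −0.001 | −0.001 |
| Depends on prior utility, same rule in both arms | −0.007 | −0.003 |
| Depends on prior utility in one arm only (stress case) | −0.088 | −0.026 |

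With no loss, the SD of the estimate is 0.020 unadjusted and 0.011 adjusted.

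Unweighted GEE was run for only 25 replicates. In the stress case the SD was about 0.025, so the Monte Carlo error is about 0.025 / √25 = 0.005. The bias there was about −0.05 with an independence working correlation and about 0 with the correct exchangeable one. Under loss completely at random it was near zero with either.

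**4. Reading the result.** Whether GEE copes depends on the mechanism, on its contrast between arms and on the working correlation, and section 10.3.6 fixes none of these. Baseline adjustment changes nothing on average when there is no loss; it gains precision.

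**The case against.** The strongest reply is that this is loose wording in a protocol that defers detail to an SAP (section 10.3). The mechanism may also be benign: under the same rule in both arms the simulated bias was small, and GEE with the right working correlation removed even the stress-case bias. Safeguards exist too. There is a reminder followed by blinded telephone completion, withdrawing participants are offered the final questionnaire, costs come from linkage, and the second benefit measure, hospitalisations avoided, needs no EQ-5D.

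Much of this stands. It limits the problem to EQ-5D and rules out saying that the analysis is biased as a fact. It does not rescue the sentence, which promises a property without the conditions that the property needs, for a quantity that GEE does not complete.

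Three stronger readings are tempting, and the documents do not support them:

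- A reader might infer that deaths are excluded. Section 10.3.6 does not say so. It promises a QALY for every person, and dates of death are collected, so utility 0 after death can be applied. Any survival effect said to be lost by dropping deaths therefore assumes a rule that the plan does not contain.
- A reader might infer that lack of baseline adjustment biases the QALY difference. Under randomisation it does not; the loss is precision and protection against chance imbalance. The section is also silent on adjustment and does not rule it out.
- A reader might take 30% as the expected EQ-5D loss. It is an upper planning figure that mixes death with withdrawal, and death is not missing data.

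**Conclusion.** The point holds in a limited form. The statement that GEE allows for missing data is wrong as a general claim, and it does not fit the per-person area-under-the-curve QALY defined in the same section. If sicker patients stop returning EQ-5D, the QALY difference can be biased, most of all if the pattern differs between arms. No size can be derived from the documents. The simulated values rest on assumed utilities and loss rules, and show only that the answer runs from negligible to large with the mechanism. The last time point is also not fixed: it could mean month 18, month 24 or a person's own last questionnaire.

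The effect is confined to the QALY side of a secondary outcome. Costs are largely protected by linkage, and the conclusions on both primary outcomes are unaffected.

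**What to change.** In section 10.3.6, delete the claim that GEE allows for missing data and state instead:

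- **Missing utilities.** Multiple imputation by arm in participants who are alive, using baseline and interim values; or inverse-probability-weighted GEE. Add a sensitivity analysis for data missing not at random, since the one-way and probabilistic analyses named do not explicitly address that.
- **Horizon and death.** QALYs over one common horizon of 18 months from randomisation, which matches the funded follow-up, with utility set to 0 from the recorded date of death. Place each questionnaire at its actual date, including a final questionnaire completed early at withdrawal.
- **Comparison.** Incremental QALYs by regression adjusted for baseline EQ-5D and the stratification factors, in line with section 10.3.2 for the other self-reported scores. Give the reason as precision and chance imbalance, not removal of bias.

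The cost is some extra analyst time. Baseline EQ-5D, interim EQ-5D and dates of death are already to be collected, so no new data are needed.

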## **11. ETHICAL CONSIDERATIONS**

### **11.1 Ethical Standards**

The investigators will ensure that this study is carried out according to the Declaration of Helsinki,[3] and the NHMRC National Statement on Ethical Conduct in Human Research (2018).[4]

### **11.2 Ethical Review**

The Protocol and all relevant documents will be submitted for approval to the PAH HREC (the lead HREC), for waiver of review by QIMR Berghofer, QUT and UQ HRECs, and to the Governance Offices at the four participating sites. Written approval will be obtained before participants are enrolled. If approval is suspended or terminated at any site, the Principal Investigator will notify the PAH HREC immediately.

It is the responsibility of the Investigator to report study progress, including a safety report, to the HREC as required or at intervals not greater than one year. Informed Consent

Before enrolment into the study, each prospective candidate will be given a full explanation of the nature and purposes of the study, and a copy of the PICF (Appendix C) to review. The site nurse will explain (either in person, telephone or web-based communication such as skype or face time) the nature of the study, its purpose, procedures, expected duration, and the potential benefits, risks and inconveniences in participation. Once the essential study information has been provided, and the Investigator is assured that the individual understands the implications of participating in the study, they will be asked to give consent to participate in the study by signing and dating the Consent Form. A note that written informed consent has been obtained will be made on the participant's CRF. The completed consent form will be retained by the Investigator and a copy will be given to the participant.

### **11.3 Blood Sampling & Communication of Genetic Results**

Participants will be asked to provide a blood sample at baseline and 6 months for future genomic analyses to evaluate associations with the study outcomes (e.g., symptoms, HRQoL, survival). Participants do not have to provide a blood sample to participate in the main PROMISE study. This part of the study is exploratory and aims to identify possible markers of HRQoL and symptom experience in this cohort.

This study will not measure known markers of disease risk so there is a low risk of identifying information that is important for participants' or other family members' health. The findings will also have no health significance to an individual participant as they already know their outcomes (e.g. symptom experience, HRQoL). Any findings from this work would need to be validated by future research before diagnostic tests for such outcomes could be developed thus any findings of potential genetic predictors of poorer outcomes would have no impact on current clinical care decisions for patients or their relatives. This part of the project is very unlikely to benefit participants or their relatives directly and the results will not be communicated with participants individually.

Although the results of the planned genetic analyses will not be communicated with participants individually there is one exception when genetic information may be communicated with participants via their nominated medical contact. In future, new markers of disease may be identified thus it is possible, although unlikely, that we may discover such information inadvertently during our genetic research. Information about a medically-

significant genetic variant may have nothing to do with a participant's reasons for taking part in the study and may involve a completely different genetic condition. Some people find the news that their family has a genetic condition to be distressing and may not wish to know that it could be present in themselves, or other family members. Participants will, therefore, be able to choose whether or not they wish to receive information about any potentially significant genetic variants. If they wish to receive this information, they will need to confirm this on their consent form when consenting to the genetic analyses. Participants will also need to nominate a medical doctor who will receive a report about what is discovered, and will pass the information back to them. A medical doctor must be involved so that the participant can be fully informed of the implications of the genetic result on their health and that of their family. Analyses will be conducted within the Genomics Research Centre at QUT and this also operates a diagnostic clinic and so can facilitate contact between the participant's doctor and specialist counsellors and geneticists who will assist in the management of any condition that is identified. Participants will also be informed that some forms of health insurance or employment might require them to reveal any results of this research that are returned to them, or whether or not they have undergone testing of any kind for a known genetic condition.

For participants who decide to provide a blood sample, there are only minimal risks (e.g. some participants may experience minor bruising or discomfort in their arm) associated with having blood taken by a trained phlebotomist. The sample will in most cases be taken during routine blood collection as part of usual follow-up care at a cancer clinic and therefore it does not pose any additional risk to the participant. If this is not possible, the blood collection will take place at a time and pathology centre convenient to the participant at no cost to the participant. The phlebotomist will take a small sample of blood (approximately 20mL) from the participant at baseline and 6 months. The blood samples will be transported to the Genomics Research Centre at QUT for processing and storage and will be used for approved projects to evaluate genetic associations with patient outcomes (e.g. HRQoL, symptom experience).

## **11.4 Protocol Amendments**

Neither the Site PI nor the Coordinating PI may modify the Protocol without first obtaining the agreement of the other party in writing. No amendments to the Protocol may be implemented without prior approval of PAH, QIMR Berghofer and other appropriate HREC(s). If a Protocol amendment requires changes to the PICF, the revised PICF must be approved by the PAH, QIMR Berghofer and appropriate site HREC(s) prior to use.

It is the responsibility of the Principal Investigator to submit the amendment to the HRECs for their approval; written approval should be obtained and a copy provided to the Sponsor. The Sponsor is responsible for determining whether or not the local regulatory authority must be notified of the Protocol change. Completed and signed Protocol amendments will be circulated to all those who were on the circulation list for the original Protocol. Any training that is required by the amendment must be provided to study staff by the Principal Investigator.

The original signed copy of amendments will be kept in the Study File with the original Protocol. Where an amendment to the Protocol substantially alters the study design or the potential risks to the participants, each participant's consent to continue participation should be obtained.

## **11.5 Protocol Deviations**

All protocol deviations and reasons for them must be recorded on the CRF and must be reported to the Principal Investigator as soon as is reasonably practicable and within 7 days of first becoming aware of the deviation. Protocol deviations will be assessed for significance by the Principal Investigator and any deemed to have a potential impact on the integrity of the study results or the ethical acceptability of the trial will be reported to the HREC. Where deviations to the protocol identify issues for protocol review, the protocol may be amended as per section 11.5.

## **11.6 Retention of Other Study-Specific Samples**

Blood samples will be kept securely at QUT. The samples and genetic material will be given a unique identification number and the participant's name will be removed to protect their privacy. Data will be stored securely and only authorised persons, who understand it must be kept confidential, will have access to it.

Samples will be retained beyond the end of the main trial (with update HREC approval as required) as the genetic analysis will continue after this. When no further projects are planned, the samples will be destroyed as per NHMRC and QUT guidelines.

## **12. DATA HANDLING, RECORD KEEPING AND PUBLICATION POLICY**

### **12.1 Data Management Responsibilities**

The study database will be maintained at QIMR Berghofer. Personal information will be kept separate from questionnaire data and access will be restricted to authorised project staff. Questionnaire data will be stored by study ID with no personal information attached and will be made available to approved project staff for analysis.

Information about the blood samples (study ID number, date of collection and processing etc.) will be stored securely at QUT. This will not include any information that would allow the lab to identify individual participants.

